## **B. Background and Significance**

Music has been shown to have an impact on the autonomic nervous system, reducing sympathetic nervous system activity leading to reduced heart rate and slowed respiration. This in turn has been associated with reduction in anxiety. Music listening also reduces acute pain during surgery, post-operative recovery, orthodontic procedures, and during the cold-pressor task (a pain induction technique) in healthy participants. A recent meta-analysis confirms that music has a positive effect on pain, anxiety, and depression in chronic pain patients. However, the impact of music listening on objective measures of pain sensitivity in patients with chronic pain have not yet been described. The goal of this pilot study is to begin to understand the possible analgesic effects of music listening on objective measures of pain sensitivity in patients with fibromyalgia.

Fibromyalgia (FM) is the second most common "rheumatologic" disorder, second only to osteoarthritis. Depending on the diagnostic criteria used, the prevalence is from 2 to 8% of the general population. With newer diagnostic criteria, the disease has a female:male ratio of 2:1, similar to other pain conditions. The prevalence is similar in different countries, cultures and ethnic groups. There is no evidence that fibromyalgia has a higher prevalence in industrialized countries and cultures. FM can be thought of as a centralized pain state. Centralized pain is a lifelong disorder that begins in adolescence or young adulthood where pain is manifested and experienced in different body regions at different times. "Centralized" refers to the amplification of pain or central nervous system origins of pain. The term does not imply that peripheral nociceptive input is not a contributor to the individuals' pain, but rather that they feel more pain than would be normally expected based on the level of nociceptive input. Not surprisingly, this "pain-prone" phenotype is best exemplified by fibromyalgia patients.

Psychological, behavioral, and social issues also contribute to the pathogenesis of fibromyalgia. Individuals with fibromyalgia are more likely to have psychiatric disorders including: depression, anxiety, obsessive-compulsive disorder, and posttraumatic stress disorder (PTSD). Several factors appear to play a role in the pathophysiology of FM: abnormal autonomic nervous and neuroendocrine system function (disordered central pain processing), genetics (familial predisposition), and environmental triggers (psychosocial/life stressors and emotional/physical trauma). Of these environmental triggers, traumatic experiences and stressful life events have been more frequently reported in FM patient cohorts compared to controls in clinical as well as population samples.

There is a growing appreciation of the importance of augmented central nervous system (CNS) pain processing and centralized pain in many chronic pain states. *The term "centralized pain" has been used to describe any CNS dysfunction or pathology that may be contributing to the development or* 

*maintenance of chronic pain*. The pain experienced by individuals with centralized pain is typically multifocal (with a high current and lifetime history of pain in many bodily regions), rated as more severe, and characterized by neuropathic pain descriptors. Beyond pain, co-existing somatic symptoms including memory difficulties, fatigue, and sleep disturbances as well as cognitive/affective symptoms (e.g., catastrophizing, anxiety, depression) are frequently observed. Another hallmark of the centralized pain phenotype is the frequent presence of hyperalgesia and/or reduced or absent endogenous analgesia. Data from quantitative sensory testing (QST) studies suggest a wide, bell-shaped distribution in pain sensitivity across the general population. Most, but not all, individuals with centralized pain fall on the right side of this curve and have QST findings consistent with notable hypersensitivity (hyperalgesia and allodynia). Some of the chronic pain conditions where QST evidence of widespread hypersensitivity is consistently seen include fibromyalgia (FM), irritable bowel syndrome, tension headache, low back pain, temporomandibular joint disorder, interstitial cystitis, and vulvodynia. We will use QST to objectively measure pain sensitivity while listening to music and while listening to nature sounds, in patients with fibromyalgia.

The analgesic effect of music is thought to occur through several mechanisms: Contextual, Cognitive, Emotional, and Physiological. First, music provides a predictable *context* that can increase the listeners' sense of control. This is further enhanced if the music is familiar, as this can bring in other effects that are not related to aspects of music specifically, such as setting up expectations and heightening nostalgia. Studies have shown the greatest analgesic effects when music is selected by participants. Second, music can serve as a *cognitive* distraction, taking attention away from the painful stimulus. This is of course not specific to music and could be achieved with other types of stimulation, such as reading or listening to nature sounds. Third, music is a powerful inducer of *emotion*. Music that is positive, liked by the listener, and low on arousal has the strongest analgesic effect. Finally, music listening interventions and music therapy have also been shown to reduce anxiety and depression. The anxiolytic effect may be due to the *physiological* effect of music on the parasympathetic nervous system, increasing the vagal response and reducing heart rate and respiration rate. Music also has effects on the brain directly, causing the release of endogenous opioids and dopamine and activating areas of the descending pain modulatory system. The specific musical characteristics that yield the greatest analgesic effects are difficult to pinpoint, as there is not a standard for reporting. Meta-analyses have revealed that music with 60-80 beats per minute, in a major key and without lyrics or percussion have the largest effects.

Previous studies in patients with FM have shown that patients have reduced self-reported pain and increased mobility after even a short, 10-minute music listening intervention. After listening to music of their choice, participants were faster in a standard mobility assessment, the timed-up-and-go task. A second study using resting state functional magnetic resonance imaging (rsMRI) confirmed the impact of a 5-minute music listening intervention on the centralized descending pain modulatory system (DPMS), identified as changes in functional connectivity between regions of the DPMS that positively correlated with changes in pain scores. Our proposed study will be the first to investigate whether objectively measured pain sensitivity is reduced by music listening.

The proposed study is **significant** as it will **identify whether music listening has an analgesic effect** during pain threshold and tolerance testing for patients with FM that supersedes any effect of auditory distraction. Results from the proposed study may provide objective evidence that **music listening objectively improves analgesia and pain management** and thus could be considered therapeutic during situations where acute pain is expected.

## C. Rationale

The proposed study is significant as it will identify whether music listening has an analgesic effect during pain threshold and tolerance testing for patients with FM that supersedes any effect of auditory distraction. Results from the proposed study may provide objective evidence that music listening objectively improves analgesia and pain management and thus could be considered therapeutic during situations where acute pain is expected.

This study is innovative as it is the first to collect objective measures of within-subject change in pain

KUMC - HRPP- 03/12/2015

sensitivity in patients with FM using controlled, quantitative measures using a music listening intervention. Additionally, we will use specific pieces of classical music, clearly described in musical terms, for the listening intervention to control heterogeneity of response based on variability in musical parameters, such as tempo or instrumentation, which may impact the analgesic response. We will also use an active control condition of nature sounds to isolate the effect of music compared to another distracting stimulus. We have assembled a research team with expertise in chronic centralized pain syndromes and use of PROs and QST for clinical pain research ([name]) and music ([name]) to develop this research project, which will be utilizing rigorous methods currently used in [name] funded NIH work as well as having a strong foundation and rationale in music theory.

## II. Research Plan and Design

Overall Study Design. For Aims 1 and 2, we will enroll 40 patients with FM to undergo QST testing on two separate days: baseline (Testing As Usual, no sound) and auditory listening. Participants will be randomized to two auditory listening conditions: music listening and nature sound listening. The conditions will be counterbalanced across subjects such that some will have listening on their first testing day and no sound on the second, and the rest of the subjects will have no sounds on the first day and listening on the second. Participants will be seated in a quiet room and a heart monitor will be attached. The participant will wear headphones during all testing sessions (including the no-sound control). They will listen to 10 minutes of the specified auditory recording (or silence) prior to QST testing. The researcher will then conduct the QST while the participant continues to listen to the auditory recording. The study visit will last for approximately 1 hour. The researcher collecting QST data will be blinded to which recording the participant is hearing.

After screening, informed eConsent (paper consent forms will be available if requested), and enrollment into the study, all subjects will undergo an evaluation which includes a battery of questionnaires for patient phenotyping that will assess symptoms including pain, physical function, depression, anxiety, and catastrophizing symptoms. QST parameters will also be performed after questionnaire administration as described above.

Patient Population. Recruitment: Participants will be recruited from the KUMC [name], Comprehensive Spine and Pain Management Center's chronic pain clinics and surgical spine clinics. The Frontiers Registry and the Pioneers Community Research Recruitment Registry services through the Frontiers: The Heartland Institute for Clinical and Translational Research will also be used to foster the recruitment of participants from the community. We will also be using web-based recruitment pathways including Craig's List, social media, and the KUMC intranet. Patients will be paid for their time for all visits.

Randomization Procedures: Participants will be randomized following eConsent using the REDCap Randomization tool. Randomization is defined using a random number generator, and stratified by gender to ensure equal numbers of males and females in each group. Audio files will be labelled with dummy codes to blind the researcher collecting the data. A file will also be created for the no-sound condition, to further keep the researcher blinded.

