This two-arm parallel randomized controlled pilot study will enroll 40 patients with fibromyalgia. Patients' pain thresholds and sensitivity will be measured using a battery of quantitative sensory tests (QST). All patients will have two testing sessions: one under testing as usual conditions with no-sound, and one while listening to either instrumental Classical music, selected by the researchers with careful consideration of the musical characteristics, or a nature sound placebo control condition. This careful experimental design will allow us to test whether music listening elicits greater analgesic effects over simple auditory distraction. To minimize potential bias we will employ sound cancelling headphones and randomization of conditions so that the researcher collecting the QST measures will be blinded to whether the patient is hearing music, nature sounds, or nothing. The proposed study is significant as it will identify whether music listening has an analgesic effect during pain threshold and tolerance testing for patients with FM that supersedes any effect of auditory distraction. Results from the proposed study may provide objective evidence that music listening objectively improves analgesia and pain management and thus could be considered therapeutic during situations where acute pain is expected

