#### II. SPECIFIC AIMS

Aim 1: Determine whether music listening during pain sensitivity testing has an analgesic effect on pain thresholds and tolerance and whether this effect is of greater magnitude in comparison to a non-musical auditory stimulus in patients with Fibromyalgia (FM). In order to accomplish this

Aim, patients with FM will undergo a variety of quantitative sensory testing (QST) procedures in order to KUMC – HRPP- 03/12/2015 Page 1 of 19 fully characterize their peripheral and central nervous system pain processing systems, including mechanical pain sensitivity and temporal summation. QST testing will be done at baseline (no auditory stimulus of any kind) and then will be repeated within the same subject while listening to the auditory stimulus. Patients will be randomized to either the Music arm or the Placebo (nature sounds) arm. Half of the patients will listen to music, and half will listen to nature sounds during testing. Hypothesis 1a: We hypothesize that both listening conditions will reduce pain sensitivity (lead to higher pain thresholds and tolerance) as compared to the no-sound control. Hypothesis 1b: We hypothesize that the use of music listening during QST tasks will reduce pain sensitivity as compared to the use of only nature sounds. Aim 2: Identify whether the objective analgesic effects of music listening are associated with subjective measures of anxiety, pain catastrophizing, resilience, and measures of music experience and enjoyment. In order to accomplish this Aim, the degree of analgesic effect of auditory listening (as measured by the difference in QST measures between baseline and music listening) will be calculated and correlated to subjective measures of pain and other pain-related patient characteristics using patient-reported outcome (PRO) measures. Hypothesis 2: We hypothesize that greater analgesic effect of music listening will be associated with lower levels of anxiety, depression, and with higher levels of music experience and enjoyment.

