Mitigation of bias: We propose to use several strategies to mitigate potential bias in this study. Participants will be randomized to experimental or placebo group, group allocation will be concealed from personnel and they will be blinded throughout testing and analysis. Patients cannot be blinded as they will know whether they are hearing nothing, music, or nature sounds during testing. Our counterbalancing of testing days will help to ensure that attrition is not affecting one condition to a greater degree than another. Finally, our strategy to avoid potential publication bias is that by having both a no-sound control and a placebo nature sound control, we will be able to determine whether a) there is an analgesic effect of distraction in this population, and b) whether that effect is greater for music over another distracting auditory stimulus.

Study Limitations and Plans to Overcome Them: Recruitment: We do not anticipate that there will be any difficulty with participant recruitment. Given the clinically significant volume of fibromyalgia patients seen at the [name], Comprehensive Spine Center, we are confident that subject enrollment will be achievable within the allotted timeframe. Also, we plan on using the innovative recruitment programs available at KUMC to assist investigators with participant recruitment including the Frontiers Registry and the Pioneers Community

Research Recruitment Registry. Our project budget includes a financial incentive for patient participation which will aid in recruitment and compliance with study procedures.

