# B. Study Type and Design:

This study is a pre-post interventional parallel randomized control trial pilot study. We will enroll 40 patients with FM to undergo QST testing on two separate days: baseline (Testing As Usual, no sound) and auditory listening. Participants will be randomized to two auditory listening conditions: music listening and nature sound listening. The conditions will be counterbalanced across subjects such that some will have listening on their first testing day and no sound on the second, and the rest of the subjects will have no sounds on the first day and listening on the second. Participants will be seated in a quiet room and a heart monitor will be attached. The participant will wear headphones during all testing sessions (including the no-sound control). They will listen to 10 minutes of the specified auditory recording (or silence) prior to QST testing. The researcher will then conduct the QST while the participant continues to listen to the auditory recording. The QST testing battery will last for approximately 1 hour. The researcher collecting QST data will be blinded to which recording the participant is hearing.

After screening, informed eConsent, and enrollment into the study, all subjects will undergo an evaluation which includes a battery of questionnaires for patient phenotyping that will assess symptoms including pain, physical function, depression, anxiety, and catastrophizing symptoms. QST parameters will also be performed after questionnaire administration as described above.

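### Session order is counterbalanced but is not in the randomisation plan and has no stated ratio; the Aim 1 test has no order term, and Specific Aims reads as a fixed order

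*Combined protocol and SAP*

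**What the plan says.** The Research Plan (Overall Study Design) and section B, Study Type and Design, describe two testing days in counterbalanced order: "some will have listening on their first testing day and no sound on the second", with the others reversed. Neither gives a number or ratio. The paragraph on mitigation of bias gives attrition as the reason: "Our counterbalancing of testing days will help to ensure that attrition is not affecting one condition to a greater degree than another".

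The Abstract says in general terms that conditions will be randomised so that the tester is "blinded to whether the patient is hearing music, nature sounds, or nothing". The Randomization Procedures paragraph supports that blinding: "A file will also be created for the no-sound condition, to further keep the researcher blinded". The only balancing factor it names is gender: "stratified by gender to ensure equal numbers of males and females in each group". It does not mention session order.

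Two places point the other way. Aim 1 in Specific Aims says "QST testing will be done at baseline (no auditory stimulus of any kind) and then will be repeated within the same subject" with the sound playing. Section B opens with "This study is a pre-post interventional parallel randomized control trial pilot study".

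Hypothesis 1a (H1a) is that "both listening conditions will reduce pain sensitivity" relative to no sound; Hypothesis 1b (H1b) is that music does so more than nature sounds. Section C plans a paired t-test or a nonparametric alternative for Aim 1, with no term for order or day. It also says that the data will supply effect sizes for a larger trial.

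**The concern.** A second session of painful testing can give different results from the first, in either direction, whatever the patient hears. In a two-day within-patient comparison, that shift is separated from the effect of sound only if order is balanced or modelled. Here balance is intended, but the section that would deliver it leaves order out, and the analysis does not use it.

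H1a is the more exposed hypothesis, because it compares the two days directly. H1b compares changes between randomised arms, so a shift common to both arms cancels when their order splits match. Any error in the H1a estimate would pass into the effect sizes for the next trial.

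**Working it through.** **Inputs from the documents.** 40 patients, half per arm, so 40/2 = 20 per arm; two sessions each; both orders used, split unstated; a paired test without an order term. The plan gives no power figure to reproduce.

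**Assumptions.** Two-sided 5% level; no dropout; a session effect π (day 2 minus day 1) of 0.1, 0.25 or 0.5 SD of the listening-minus-no-sound change. H1a is taken as a paired test in each arm and H1b as a between-arm comparison of changes, because section C spells out neither.

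**Model.** Change = τ + π·o + e, with o = +1 if listening is second, -1 if first, and SD(e) = 1. Let p be the share of an arm with listening second.

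- H1a shift = (2p - 1)π. At 10:10 it is 0. At 14:6 it is (2 × 0.7 - 1)π = 0.4π, that is 0.04, 0.10 and 0.20 SD.
- H1b shift = 2(p_music - p_nature)π. It is 0 when the splits match. With 13 against 7 listening second it is 2(0.65 - 0.35)π = 0.6π.
- At 10:10 without an order term, the variance of the changes is inflated to 1 + π²: 1.0625 at 0.25 SD and 1.25 at 0.5 SD. The test becomes conservative.

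**Simulated type I error and power, no order term**

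| Setting | π = 0.1 | π = 0.25 | π = 0.5 |
|---|---|---|---|
| H1a error, 10:10 | 5.0% | 4.4% | 3.0% |
| H1a error, 12:8 | 5.0% | 4.8% | 4.4% |
| H1a error, 13:7 | 5.1% | 5.7% | 6.5% |
| H1a error, 14:6 | 5.1% | 6.5% | 9.7% |
| H1b error, 13 vs 7 | 5.3% | 6.6% | 10.6% |
| H1a power, 10:10 (true effect 0.660 SD) | 80% | 78% | 72% |
| H1b power, 10:10 (true difference 0.909 SD) | 80% | 78% | 73% |

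**Chance imbalance.** If order is a coin toss, Binomial(20, 0.5) gives 13:7 or worse with probability 0.263 in a given arm, and 1 - (1 - 0.263)² = 0.457 in at least one arm. For 14:6 or worse in a given arm it is 0.115. Averaged over all splits, H1a type I error is 5.0%.

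**With an order term.** Type I error is about 5% at every split tried. At 10:10, power is about 80% for both hypotheses at every π, using a within-arm model for H1a.

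**Cost of uneven order once adjusted.** The variance of the within-arm H1a estimate is 1/[20(1 - m²)], where m = 2p - 1. At 10:10 it is 0.0500; at 14:6 it is 1/(20 × 0.84) = 0.0595, 19% higher.

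**The case against.** The best defence is that the plan does imply random order. Randomising arm alone could not blind the tester to silence versus sound, so the Abstract's statement about randomised conditions is most naturally read as covering order. That stands. A reader might infer that order is left to scheduling or convenience, which would be real bias, but the documents do not support this. The gap is that the randomisation section does not carry the intention out.

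A reader might also infer from Specific Aims and the pre-post label that no-sound always comes first. H1a would then be wholly confounded with session, with type I error of 56% per arm at an assumed 0.5 SD. The documents do not support that either. Counterbalancing is stated in three places, a dummy no-sound file would achieve little if silence were always on day 1, and the plan uses baseline as a name for the no-sound condition in the same sentences that lead into counterbalancing. The conflict is one of wording, but it does need resolving.

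Finally, the effect is small under likely conditions. At 12:8 the error does not exceed 5.0%, and about 10% needs both a 14:6 split and a 0.5 SD session effect. At 14:6 and 0.25 SD the shift of 0.10 SD is under half the standard error of 1/√20 = 0.22. This is also a pilot with no power claim. All of that is fair and limits the weight of the point. It does not remove the power loss at exact balance, or the case for a remedy that costs almost nothing.

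**Conclusion.** The point holds as a cheap improvement. Order is not specified as a randomised or balanced factor where randomisation is described, no ratio or within-arm balance is given, one section reads as a fixed order, and the Aim 1 test has no order term.

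With 10:10 order the consequence is lost power only: from 80% to about 78% at a 0.25 SD session effect and 72% at 0.5 SD. With uneven order, H1a shifts by (2p - 1) times the session effect; at 14:6, type I error is about 6.5% and 10%. H1b shifts only if the split differs between arms. Under coin-toss order this is chance error in the one trial run, not systematic bias.

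The conclusion rests on an assumed session effect, a two-sided 5% level and assumed forms of the H1a and H1b tests. With no session effect there is no bias.

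**What to change.** 1. Reconcile the Aim 1 wording in Specific Aims and the pre-post label in section B with the counterbalanced design.
2. Randomise order 1:1 within each arm in the same REDCap list, about 10 patients per arm-by-order cell. Balance order within gender only if numbers allow: arm by order by gender gives 40/8 = 5 per cell even with equal sexes, and the plan expects equal sexes to be hard to reach.
3. For H1a, within each arm, regress the listening-minus-no-sound change on order coded +1 (listening second) and -1 (listening first), and test the intercept with that arm's own variance (18 df). Do not mean-centre the order code: with both arms at 14:6 that leaves the shift in place, with type I error of about 14% at 0.5 SD. Do not pool variance across arms: at an SD ratio of 1.25 the error in the more variable arm is about 7.7%.
4. For H1b, test the arm term in a regression of change on arm and order (37 df).
5. If a nonparametric test is used, make it account for order too.
6. State the assumptions: no carry-over between days and, for H1b, the same session effect in both arms.

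The cost is one degree of freedom per test (19 to 18 for H1a, 38 to 37 for H1b) and a revised allocation table, with no extra patients or visits. If enrolment has begun, the order term helps only if both orders have been used, and uneven order costs some precision (19% more variance for H1a at 14:6).

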## C. Sample size, statistical methods, and power calculation

Statistical Analysis: Data analysis will be performed by the KUMC Department of Biostatistics. The data analyst will also be blinded to whether data was during the nature sounds or music listening condition. Once all data have been collected and summary scores have been calculated, the database will be locked. Only then will the blind be broken for whether the QST scores were associated with music or nature sounds, and the final statistical test will be conducted.

Aim 1 Analyses: Pain thresholds and temporal summation scores will be treated as continuous measures and normality will be assessed prior to analysis. QST data will be analyzed using a paired t-test or appropriate nonparametric test to detect changes within-subject changes in QST measures between nature sounds or music listening.

Aim 2 Analyses: Magnitude of changes in QST measures between nature sounds and music listening will be calculated and correlated to the subjective measures of pain and music that are administered via patient-reported outcome questionnaires. All measures will be treated as continuous measures and normality will be assessed prior to analysis. These relationships will be analyzed using Pearson's correlation testing.

Sample size for Study Procedures in Aims 1 and 2: It is not possible to conduct adequate power analyses for the aims as this pilot study will be the first to measure QST changes with a music listening intervention in this patient population. Sample sizes for studies included in previous meta-analyses ranged from 25 to 175. We will use the data collected in this pilot study to estimate effect sizes for the next application for a larger trial.

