### Women and Minority Inclusion in Clinical Research

**Inclusion of women:** Women are included in all studies described. We will try to expect approximately equal gender distribution in the enrolled participants, however, fibromyalgia is more prevalent in women which may make recruitment of equal gender distribution difficult to attain.

*Inclusion of minorities:* All minority groups are encouraged to participate in this and all our research projects. In 2003, the University of Kansas Medical Center's outpatient population was composed of 18% African-American, 10% Hispanic, 1% Asian, and 3% other. We expect this proportion of minorities will be reflected in our enrollment.

*Exclusion of Children:* The tests and interventions would be quite invasive and demanding for children. Therefore, children are not included in the present study.

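### The plan stratifies by gender to secure balance but states no restriction within gender, and then uses gender in no analysis

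*Combined protocol and SAP*

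**What the plan says.** The Abstract sets the size: "This two-arm parallel randomized controlled pilot study will enroll 40 patients with fibromyalgia". The Specific Aims set the ratio: "Half of the patients will listen to music, and half will listen to nature sounds during testing".

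The allocation method is described in one place, the Randomization Procedures paragraph of section II: "Participants will be randomized following eConsent using the REDCap Randomization tool", followed by "Randomization is defined using a random number generator, and stratified by gender to ensure equal numbers of males and females in each group". No section mentions blocks, minimisation or any other restriction. None says that the sequence is unrestricted.

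Two passages bear on the gender mix. Section I.B states that "the disease has a female:male ratio of 2:1". The section on inclusion of women aims for roughly equal numbers but concedes that "fibromyalgia is more prevalent in women which may make recruitment of equal gender distribution difficult to attain".

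The only detailed analysis text is section II.C. For Aim 1, "QST data will be analyzed using a paired t-test or appropriate nonparametric test"; for Aim 2, it gives Pearson correlation. Neither includes gender, although the Demographics item calls sex an important biological variable to investigate. Section V.A adds only the timing of the analyses.

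**The concern.** Two things do not join up.

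First, the plan attributes balance to stratification. Separate unrestricted random sequences for men and women are together the same as one unrestricted sequence. The balance comes from the restriction within stratum, which is the part left unstated. The promised outcome is also ambiguous. It may mean as many men as women inside each arm, or each gender divided evenly between the arms.

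Second, gender is important enough to stratify on but appears in no analysis. The comparison affected is Hypothesis 1b, music against nature sounds, which is the contrast that the randomisation supports. When allocation is balanced on a factor that predicts the outcome and the analysis omits it, the standard error is too large. The trial then pays for the balance without collecting the precision. In a pilot of 40 whose stated use is to estimate effect sizes for a larger trial, that means wider intervals than the data warrant.

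**Working it through.** The plan gives no power calculation, alpha, SD or effect size, so there is no stated figure to reproduce. Inputs from the documents are n = 40, 1:1 allocation and a 2:1 female to male ratio. Assumptions are marked as such.

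**1. Which reading of the promise can allocation deliver?** Equal men and women inside an arm requires equal enrolment of each. At 2:1, 40 × 2/3 ≈ 27 women and 13 men, and no allocation method makes such arms half male. Only the other reading, each gender divided evenly between arms, is within the randomisation's control.

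**2. Balance if the list is simple 1:1 randomisation (conditional, not stated in the plan).** The number allocated to music is X ~ Binomial(40, 0.5).

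- P(X = 20) = C(40,20)/2^40 = 0.125.
- Arm gap of 6 or more: P(X ≤ 17) + P(X ≥ 23) = 0.430.
- Both genders exactly even, with 20 women and 20 men: [C(20,10)/2^20]² = 0.176² = 0.031.
- Both genders exactly even, with 26 women and 14 men: 0.155 × 0.209 ≈ 0.032.
- With 13 men, P(9:4 or worse) = 0.267. With 27 women, P(gap of 5 or more) = 0.442.

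**3. Balance if the list is blocked within gender.** An unfinished block leaves a gap of at most half the block size in each gender. Blocks of 2 give at most 1 per gender and 2 overall; blocks of 4 give at most 2 per gender and 4 overall.

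**4. Cost of unequal arm size alone.** Efficiency relative to 20/20 is 4ab/40². For 16/24 this is 4 × 16 × 24/1600 = 0.96. The effect detectable with 80% power (two-sided alpha 0.05, assumed) moves from 0.91 to 0.93 SD, which is small.

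**5. Cost of omitting gender under balanced allocation.** Let gender shift the change score by g SD, and let p be the share of men. Balance removes gender from the difference in arm means. The pooled within-arm variance still contains it, rising from 1 to about 1 + g²p(1 − p). With p = 0.5, the standard error is inflated by about √(1 + 0.25 × 0.25) = 1.03 at g = 0.5 and √(1 + 1 × 0.25) = 1.12 at g = 1.0.

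Simulation of a two-sample t-test on change, with each gender split exactly evenly between arms, shows the effect. Assumptions: two-sided alpha 0.05 and a 0.9 SD arm effect for power; 20,000 runs for type I error and 10,000 for power. Simulation error is about √(0.05 × 0.95/20,000) = 0.0015 and √(0.8 × 0.2/10,000) = 0.004.

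| Women/men | g (SD) | Type I, no gender term | Type I, with term | Power, no gender term | Power, with term |
|---|---|---|---|---|---|
| 20/20 | 0 | 0.051 | 0.051 | 0.795 | 0.794 |
| 20/20 | 0.5 | 0.046 | 0.053 | 0.775 | 0.795 |
| 20/20 | 1.0 | 0.027 | 0.048 | 0.711 | 0.790 |
| 26/14 | 0 | 0.048 | 0.048 | 0.788 | 0.788 |
| 26/14 | 0.5 | 0.044 | 0.049 | 0.777 | 0.795 |
| 26/14 | 1.0 | 0.028 | 0.047 | 0.726 | 0.794 |

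The power loss is about 2 points at 0.5 SD and 7 to 8 points at 1.0 SD. The term costs essentially nothing when gender has no effect.

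**6. The same simulation under simple randomisation.** Type I error without the term stays near nominal (0.048 to 0.052). With the term, power changes by about −1 point at g = 0, +1 to +2 points at 0.5 SD and +8 to +9 points at 1.0 SD.

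**The case against.** The strongest reply is that the protocol never says the list is unblocked. A random number generator can produce a permuted-block list, and the sponsor may have one. That stands. A reader might infer that the allocation is simple randomisation, or that the plan claims a property its method lacks, but the documents are silent. The 12.5% and 43% describe what follows if no restriction was used.

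A reader might also infer that the plan promises 20 men and 20 women and will almost surely miss. It does not clearly promise that, and it discloses that an even mix "may make recruitment of equal gender distribution difficult to attain".

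Third, each patient is compared with their own no-sound session. A gender difference in the level of pain sensitivity therefore cancels, and gender matters to Hypothesis 1b only if it alters the response to sound. The documents give no evidence or size for that. This stands too, and it is why the power loss is conditional. It also answers the tempting claim that leaving gender out confounds the comparison or inflates type I error: chance imbalance under randomisation is not systematic bias, and step 5 shows a conservative test.

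Finally, a gender term cannot simply be added, because II.C contains no between-arm model. It describes a paired test for music against nature sounds, although each patient hears only one of them. That is correct, so the fix has to supply the model.

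What remains is that the means of achieving the stated balance is not given, the sentence needs rewording on either reading, and no analysis uses the stratification factor.

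**Conclusion.** The point holds in a limited form. The assurance of balance cannot be verified as written, because stratification needs a restriction within gender and none is specified. The sentence can promise only balance between arms within each gender. Should the list be simple randomisation, the chance of exactly 20/20 is 12.5% and of an arm gap of 6 or more is 43%. Unequal arm size alone would still cost little.

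The firmer part is the analysis. Gender is a stratification factor and appears in no planned test. Under balanced allocation the consequence is a conservative music versus nature comparison and some lost power, not a false-positive risk. At an assumed 0.9 SD arm effect and two-sided alpha of 0.05, the loss is about 2 points if gender shifts the change score by 0.5 SD and 7 to 8 points at 1.0 SD. It is nil if gender has no effect on change. All of those effect sizes are assumptions, since the documents give none.

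**What to change.** 1. **Analysis.** In II.C, specify Hypothesis 1b as a between-arm comparison of each patient's change from the no-sound session, for example a linear model for change with terms for arm and gender. The term costs one degree of freedom, but writing the model replaces the present test for this hypothesis. It can be done at any time before the blind is broken at database lock.
2. **Allocation.** State how the REDCap list is generated: permuted blocks within each gender, with block sizes concealed from recruiting staff. If the list is already blocked, this is one sentence; if not, a new list is needed before enrolment. A small imbalance from unfinished blocks will remain, at most 2 per gender with blocks of 4.
3. **Wording.** Replace the assurance in Randomization Procedures with a statement that stratification is used to balance the arms within each gender, and leave the overall gender mix to the recruitment section.
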